7.6 Serious Adverse Event Reporting

Any SAE that occurs after a subject signs an informed consent form through the follow-up visit (or at the time a subject is determined to be ineligible for the study or who does not enroll in the study), regardless of causal relationship, must be reported to the Sponsor within 24 hours of the investigator's knowledge of the event.

To report an SAE, complete and fax the Serious Adverse Event Report Form to the following:

[REDACTED]

For medical questions regarding an SAE, contact the Sponsor medical monitor by telephone as follows:

[REDACTED]

For fatal or life-threatening events, also fax copies of hospital case reports, autopsy reports, and other documents when requested. Additional information may be requested from the investigator to ensure the timely completion of accurate safety reports.

An SAE may qualify for reporting to regulatory authorities if the SAE is possibly attributable to the study drug and is unexpected/unlisted based on the current Telavancin Investigator's Brochure. In this case, all investigators will receive notification of the event. The investigator is responsible for notifying the Institutional Review Board or Ethics Committee and documenting the notification, as required by local regulatory authorities and in accordance with the local institutional policy.

7.7 Adverse Event Follow-up

A subject experiencing an AE or SAE will be followed by the investigator or his/her trained delegate(s) through the follow-up visit or until the investigator and/or the Sponsor has determined that the AE or SAE has resolved or a stable clinical endpoint is reached,

whichever is longer. The Sponsor may request follow-up of certain adverse events until resolution and documentation of assessments made during this period.

The investigator must take all therapeutic measures necessary for resolution of an SAE. Any medications necessary for treatment of the SAE must be recorded in the concomitant medication section of the case report form.

8 STATISTICAL CONSIDERATIONS

8.1 Analysis Objectives

The principal objectives of this study are to characterize the PK and assess the safety and tolerability of telavancin after a single dose in pediatric subjects (> 12 months to 17 years).

8.2 Sample Size and Power

The standard regulatory requirement for sample size in pediatric studies is to prospectively power to target a 95% confidence interval within 60% and 140% of the geometric mean estimates of clearance (CL_p) and the volume of distribution (V_{dss}) in each pediatric subgroup with at least 80% power.

Sample size for each pediatric age subgroup was determined on the basis of the variability in telavancin PK parameters from adult data. Data from all Phase 1 telavancin studies (eight studies, which included a total of 236 healthy subjects without infection) conducted by the Sponsor were used to estimate variability using two different methods (based on either a noncompartmental analysis or a population PK modeling approach), as outlined in Wang et al {1}. The corresponding sample size intended for PK analysis was calculated using the estimated variability.

- 1) Based on noncompartmental analysis: Determine variability from any prior relevant study by calculating the standard deviation (SD) of the natural log-transformed individual clearance (CL) and volume of distribution at steady state (V_{dss}). Noncompartmental analysis of data from the Phase 1 trials resulted in SDs of 0.27 and 0.21 for CL and V_{dss} , respectively.
- 2) Based on population PK modeling: Estimate the SD based upon the between-subject variability (BSV) found in the population PK model. The BSVs in the population PK model {2} were used, ie, 29% and 23% for CL and V_1 , respectively. The corresponding estimates of the SDs derived from the BSVs were 0.284 and 0.227 for CL and V_1 , respectively.

Using the most conservative estimate of SD (0.284 for CL derived from the population PK model), a sample size of seven per age subgroup is deemed sufficient to meet the aforementioned requirements with at least 80% power. In anticipation of possible drop-outs or missing samples, eight subjects will be enrolled in each age subgroup, which will result in

a total of approximately 30 male and female infants, children and adolescents participating in this study:

- Adolescents (12-17 years), N=8
- Older Children (6-11 years), N = 8
- Younger Children (2-5 years), N = 8
- Infants >12 and < 24 months, N = 6

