3.3 Selection of Dose and Duration of Treatment

Infants, children, and adolescents will receive a single intravenous (IV) telavancin dose infused over approximately 60 minutes. The initial starting dose of 10 mg/kg for the first eight subjects is the approved dose for treatment of complicated skin and skin structure infections (cSSSI) and treatment of hospital-acquired and ventilator-associated bacterial pneumonia (HABP/VABP) caused by susceptible isolates of *Staphylococcus aureus* in adult patients with creatinine clearance >50 mL/min.

Dose selection for the current study was based upon the current approved dose in adults (10 mg/kg), preclinical data, and simulations of the anticipated plasma exposure to telavancin in pediatric patients based on the adult telavancin population PK model and allometric scaling of telavancin clearance and volume of distribution to pediatric patients.

The effect of telavancin was evaluated in juvenile rats in a repeated-dose toxicity study. Based on these results, the effects of telavancin on juvenile animals did not differ

substantively from the effects in adults. A summary of the juvenile toxicology data may be found in the current version of the telavancin IB.

Clearance and volume of distribution were scaled allometrically from the adult population PK model across the pediatric age and weight range on the basis of an assumed allometric exponent of 0.75 (clearance) and 1.0 (volume of distribution), respectively.

Pediatric PK simulations were conducted utilizing a uniform distribution of body weights between 9.6 kg (average weight of a 1-year old child, based on WHO growth standards) and 70 kg. The distribution of creatinine clearance (CrCL) values was taken from the observed distribution of subjects in the adult population PK model and constrained to ≥ 50 mL/min in accordance with the study protocol. The age of each subject in the simulations was estimated by utilizing the average weight vs. age from the Centers of Disease Control and Prevention (CDC) growth charts for children in the United States {3}. Additionally, the values of CrCL for subjects 1 to 2 years of age were reduced by 15% to reflect dependence of renal function on size, organ maturation, and body composition {4}.

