PK simulations for a pediatric dataset of 1500 subjects ($n = 200$ simulations per subject) and dose of 10 mg/kg were conducted using the population PK model and categorized by the age stratification that is defined in the protocol (Table 3). The mean and standard deviation of exposures (area under the curve [AUC]) in the pediatric population are anticipated to be lower than the 864 ± 285 $\mu\text{g}\cdot\text{hr}/\text{mL}$ observed at day 4 in the Phase 3 adult population (Studies 0015, 0017, 0018, and 0019) after a dose of 10 mg/kg (18 to 65 years of age, $n = 393$).

The selected dose level (10 mg/kg) is therefore anticipated to maintain plasma exposure to telavancin at comparable or lower levels than previously observed in the adult population. The results of this study will be utilized to design dosing algorithms in pediatric patients intended to maintain comparable exposures to the approved dose in adults. The appropriateness of the 10 mg/kg dose will be evaluated after enrollment of Cohorts 1-4.

Table 3: Exposures to Telavancin Based on a Population Pharmacokinetic Model in Pediatric (Predicted) and Adult (Actual) Subjects

Age Range	Estimated AUC ₀₋₂₄ (µg·hr/mL) (Mean ± SD)
Adult*	864 ± 285*
12 – 17 years	628 ± 214
6 – 11 years	537 ± 185
2 – 5 years	457 ± 160
1 – 2 years	433 ± 155

* Observed exposure on day 4 from Phase 3 clinical data (n = 393)

Note: Simulations based on a total of 300,000 simulated subjects at a telavancin dose of 10 mg/kg

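### The planning SD in Section 8.2 (0.284) is smaller than the spread in the protocol's own Table 3 (about 0.33 to 0.35); at that spread the eighth child in Cohorts 1-3 is needed, not spare

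*Combined protocol and SAP*

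**What the plan says.** Section 8.2 gives the regulatory standard as to "prospectively power to target a 95% confidence interval within 60% and 140% of the geometric mean estimates of clearance" and of volume of distribution, "in each pediatric subgroup with at least 80% power".

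It says openly that variability comes from adults. The noncompartmental SDs are 0.27 (CL) and 0.21 (Vdss). The population model's between-subject terms are "ie, 29% and 23% for CL and V_1 , respectively", which convert to 0.284 and 0.227. It then concludes: "Using the most conservative estimate of SD (0.284 for CL derived from the population PK model), a sample size of seven per age subgroup" is enough for at least 80% power. Eight are to be enrolled per group to allow for drop-outs or missing samples, although the list that follows gives infants N = 6. The synopsis repeats the standard, the adult basis and the group sizes.

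Section 3.3 describes the simulation behind Table 3. It starts from the adult population model, scales clearance and volume by weight, and draws creatinine clearance from the adult model population, "constrained to ≥ 50 mL/min in accordance with the study protocol". The table note reads: "Simulations based on a total of 300,000 simulated subjects at a telavancin dose of 10 mg/kg". The AUC0-24 rows (mean ± SD, µg·hr/mL) are 628 ± 214 (12-17 years), 537 ± 185 (6-11), 457 ± 160 (2-5) and 433 ± 155 (1-2). The observed adult Phase 3 row is 864 ± 285.

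Section 8.5.6 plans 95% CIs for the PK parameters by age group, using noncompartmental methods, population methods or both.

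**The concern.** At a fixed mg/kg dose, AUC varies as the inverse of clearance per kg, so the relative spread of one is roughly the relative spread of the other. Section 8.2 plans on 29%. Section 3.3 projects 34% to 36% for the children this study will enrol. Two sections of one protocol therefore hold different values for the quantity that drives the sample size, and the power statement uses the smaller.

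With seven or eight subjects per group, a modest change in SD matters. At stake is whether seven profiles meet the stated precision, and so whether a group can lose one child and still meet it. The Safety Data Review Committee may recommend expanding a cohort (Section 6.5), and it should judge that against a realistic precision figure.

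**Working it through.** **Inputs.** Criterion 60% to 140%, 95% CI, 80% power, SD 0.284 and n = 7, all from Section 8.2. AUC means and SDs from Table 3.

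**Power formula.** On the log scale the CI half-width is t(0.975, n-1) × s/√n. It must not exceed the smaller of ln 1.4 = 0.3365 and -ln 0.6 = 0.5108, so the upper limit binds. The largest acceptable sample SD is L = 0.3365 × √n / t, and

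power = P[χ²(n-1) ≤ (n-1) × (L/SD)²].

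**The plan's own figure.** √ln(1 + 0.29²) = 0.284, as stated. For n = 7, t = 2.447 and L = 0.3365 × 2.646 / 2.447 = 0.364. Then 6 × (0.364/0.284)² = 9.85, and P[χ²(6) ≤ 9.85] = 86.9%. With n = 6 the result is 72.8%, and with n = 8 it is 95.0%. Seven is the smallest n that reaches 80%, as the plan says. A simulation with 400,000 draws also gave 86.9% at n = 7.

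**Tolerance at n = 7.** The 80th percentile of χ²(6) is 8.558. The largest SD that keeps 80% power is 0.364 / √(8.558/6) = 0.305.

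**SDs implied by Table 3.** CV = SD/mean, and log SD = √ln(1 + CV²).

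| Row | CV | log SD | n = 6 | n = 7 | n = 8 |
|---|---|---|---|---|---|
| 12-17 years | 0.341 | 0.331 | 54% | 70.0% | 82.9% |
| 6-11 years | 0.345 | 0.335 | 53% | 68.7% | 81.8% |
| 2-5 years | 0.350 | 0.340 | 51% | 66.7% | 80.0% |
| 1-2 years | 0.358 | 0.347 | 48.8% | 63.9% | 77.5% |
| Adult Phase 3 | 0.330 | 0.321 | 58% | 73.8% | 86.0% |

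Every row exceeds 0.305. The smallest n for 80% is 8, 8, 8 and 9 in the four pediatric rows. At planned enrolment, Cohorts 1-3 (eight each) have 82.9%, 81.8% and 80.0%, and Cohort 4 (six) has 48.8%.

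**AUC0-24 as a stand-in for dose/CL.** At steady state the two agree. If Table 3 is a single-dose AUC0-24, cutting off at 24 hours damps the effect of clearance. In a one-compartment approximation with half-life T, let x = 24 × ln 2 / T. The elasticity of AUC0-24 to CL is then -(1 - x·e^(-x)/(1 - e^(-x))). This gives -0.70 at the adult half-life of 8.1 h and -0.88 at an assumed 5 h. The SD of log CL behind a given AUC spread would then tend to be larger than the table shows, so the power figures above would be optimistic.

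**The case against.** The other side has several sound points.

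- **No calculation error.** The sample size follows from the stated SD. In context, the conservatism claim ranks only the four SDs listed in Section 8.2, and 0.284 is the largest of them.
- **Source of 0.284.** A reader might infer that it describes only healthy adults, because Section 8.2 introduces both methods with data from "236 healthy subjects without infection". But the SD used comes from a published population model whose title in the reference list covers infected patients as well as healthy subjects. The documents do not support saying that it excludes patients.
- **Table 3 is not pediatric data.** A reader might infer that it gives the true SD in eligible children. It is a simulation using adult creatinine clearance values, cut at 50 mL/min, whereas eligibility is per 1.73 m² by the Schwartz equation. Weight within an age group explains little of the excess: about 0.02 to 0.05 on the log scale, under assumed weight bands and the 0.75 exponent. The excess over 0.284 is √(0.331² - 0.284²) = 0.17 to √(0.347² - 0.284²) = 0.20. It must come mainly from the creatinine clearance distribution or from components that Section 3.3 does not describe.
- **Between-subject term versus total spread.** A population analysis with covariates could remove part of the extra variation, and the between-subject term would then be the more relevant SD.
- **Safeguards.** Section 6.7.2 replaces subjects whose PK is not evaluable after a serious protocol violation and allows other replacements. It does not replace subjects who discontinue for an adverse event. The committee may also recommend expanding a cohort.

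These points limit the claim but do not restore the n = 7 statement. Section 8.5.6 plans CIs by age group and allows noncompartmental estimation. An unadjusted CI of that kind carries the total spread, and the protocol's only projection of that spread in children is Table 3.

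**Conclusion.** The point holds as an inconsistent planning input. For unadjusted by-age CIs at the Table 3 spread, seven evaluable children give about 67% to 70% in Cohorts 1-3, against the stated minimum of 80%. The planned eight give about 80% to 83%. So the planned enrolment in Cohorts 1-3 still meets the target, but only with all eight evaluable. A reader might infer that those cohorts are under-enrolled; the figures do not show that. They show that the drop-out margin is used up, and in the 2-5 year group there is none left.

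Cohort 4 at six gives about 49% at its Table 3 SD. It also misses 80% at the plan's own SD (73%), so that shortfall does not depend on Table 3.

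The figures assume log-normal AUC, AUC proportional to 1/CL per kg, and no covariate adjustment. If Table 3 is a truncated single-dose AUC, the first two groups of figures would be lower; if covariates explain much of the spread, power would be higher.

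**What to change.** In Section 8.2:

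1. Limit the statement that 0.284 is the most conservative SD to the adult estimates listed there.
2. Add the precision at the Table 3 spread (log SD about 0.33 to 0.35) for unadjusted by-age CIs: about 67% to 70% with seven and 80% to 83% with eight in Cohorts 1-3, and about 49% with six in Cohort 4. Give the assumptions.
3. Say that at this spread eight evaluable profiles are needed in Cohorts 1-3, so the eighth child is not a drop-out reserve.
4. Do not claim at least 80% for Cohort 4.

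Bring the sample size text in the synopsis into line. The cost is a few sentences and a less favourable stated power. No extra enrolment is asked for, and the planned analysis does not change.

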Reference Therapy, Dose, and Route of Administration; Regimen; Duration of Treatment: Not applicable

Study Evaluations

Safety Assessments:

Subject safety will be monitored during the study using standard measures, including physical examinations, vital signs, 12-lead ECGs, clinical laboratory assessments, urinalysis, concomitant medication usage, and adverse event reporting.

Pharmacokinetic Assessments:

Blood samples for PK assessment will be taken as follows: 1.0 hour (± 5 min), 1.5 hours (± 5 min), 2 hours (± 5 min), 6 hours (± 30 min), 12 hours (± 30 min) and 24 hours (± 30 minutes) after the beginning of the infusion. The timing of PK sampling may be optimized after the completion of the older age groups (Cohorts 1-3) to assure that the minimum numbers of samples are collected in the youngest age group > 12 months to < 24 months. Plasma exposures that will be compared to adult exposures are the primary assessment for this study.

PROTOCOL SYNOPSIS (CONTINUED)

Plasma will be assayed for the determination of telavancin and the primary metabolite (AMI-11352).

Statistical Methods:

Sample Size:

The standard regulatory requirement for sample size in pediatric studies is to prospectively power to target a 95% confidence interval within 60% and 140% of the geometric mean estimates of clearance (CL_p) and volume of distribution (V_{dss}) in each pediatric age subgroup with at least 80% power.

Approximately 30 male and female infants, children, and adolescents will be enrolled into the study.

The subjects entered will be stratified by age:

- Adolescents (12 to 17 years), N= 8
- Older Children (6 to 11 years), N = 8
- Younger Children (2 to 5 years), N = 8
- Infants > 12 and < 24 months, N = 6

Sample size for each pediatric age subgroup was determined on the basis of the variability in telavancin PK parameters from adult data.

Study Endpoints:

The primary study analysis variables are the telavancin PK parameters: C_{max} , T_{max} , AUC_{0-t} , AUC_{0-inf} , and $t_{1/2}$ (as appropriate) derived from plasma concentration-time data.

The secondary endpoints are safety variables (see Safety Assessments above).

Analysis:

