3 STUDY DESIGN

3.1 Overview

This is an open-label study of the pharmacokinetics and safety of a single intravenous dose of telavancin in pediatric subjects, aged > 12 months to 17 years, who require systemic antibiotic therapy or prophylaxis for a known or suspected bacterial infection. Pediatric subjects will be enrolled by age as follows:

1. Adolescents (12 to 17 years)
2. Older Children (6 to 11 years)
3. Younger Children (2 to 5 years)
4. Infants (>12 and < 24 months)

Subjects' age will be based on their last birthday.

- Approximately eight subjects will be enrolled in Cohorts 1, 2 and 3 and approximately 6 subjects will be enrolled in Cohort 4. All 4 cohorts will be enrolled in parallel (simultaneously). The first eight (8) subjects (Cohort 1) will receive a single 10 mg/kg dose of IV administered telavancin. After the enrollment of the first 8 subjects and respective data are available, the population PK model will be refined and estimates of telavancin PK exposure will be generated for each subject. These estimates will then be compared to those observed historically in adults to facilitate adjustment of the pediatric dosing strategy, as necessary. PK data in patients recruited to date indicate that exposure to telavancin is consistent with initial modeling analysis and decreases with decreasing body weight. Therefore, the current dose is not expected to result in increased exposure in younger subjects with lower body weights. The Safety Data Review Committee (SDRC, Section 6.5) will make an integrated assessment of the safety, tolerability and available PK data after enrollment of approximately every 8 subjects for Cohorts 1-3 and after approximately 6 subjects for Cohort 4. .

Once a subject meets protocol eligibility, a single intravenous dose of telavancin will be administered over approximately 60 minutes on Day 1. Subjects will be followed for 24 hours for PK and safety assessments and will complete the study after a safety follow-up evaluation on Day 8 (\pm 1 day).

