6.5 Safety Data Review Committee

A Safety Data Review Committee (SDRC) will be composed of internal Sponsor personnel only, including the Cumberland Clinical Study Director, the Medical Monitor, the statistician and the PK scientist. Additional members may be added as needed at the discretion of the Clinical Study Director.

An SDRC meeting will be held after the enrollment of approximately every 8 subjects for Cohorts 1-3 and after approximately 6 subjects for Cohort 4. Data from these subjects has to be completed and available before the meeting. The SDRC will also meet if a Stopping Rule is met (Table 4). Available safety data, including demographic data, ECG results, vital

signs, adverse events, and laboratory results, and any available PK data will be reviewed at each meeting. Additional meetings will be scheduled as needed to review safety and available PK data.

As enrollment in Cohorts 1, 2, 3 and 4 may be ongoing during the SDRC, the SDRC may recommend that the study continues without modification; dosing adjustments; a cohort be expanded; or that dosing be discontinued.

Table 4: Stopping Rules

Scenario	Action

Any occurrence of a suspected telavancin-related moderate adverse drug reaction of the same system class (eg, cardiovascular) observed in two or more subjects
 
* Exception: red man syndrome, local site reactions,
	
 • Stop dosing additional subjects and convene SDRC (if event occurs outside the regularly scheduled review). • Review AE and all relevant safety data for evidence of relationship to treatment and clinical or medical significance. • Upon unanimous decision by the SDRC, one of the following decisions may be made: 
 – Discontinue enrollment – Continue enrollment 
** If moderate red man syndrome is observed in at least two subjects, then the rate of telavancin infusion will be decreased by 50% for subsequent subjects

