6.7.2 Subject Replacement

Subjects who discontinue the study due to an AE will not be replaced. Subjects with serious protocol violations where PK is not evaluable will be replaced. Subjects discontinued for other reasons may be replaced at the Sponsor's discretion.

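### Section 8.2 sizes each age subgroup at seven and promises eight, but plans six infants; at six the power for CL is about 73%, not at least 80%

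*Combined protocol and SAP*

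**What the plan says.** Section 8.2 (Sample Size and Power) applies the 60% to 140% target, with at least 80% power, to CL and Vdss in each pediatric subgroup. From Phase 1 adult data it takes two sets of log-scale SDs:

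- noncompartmental: 0.27 for CL and 0.21 for Vdss
- population PK model: 0.284 for CL and 0.227 for V1, converted from between-subject variabilities of 29% and 23%

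It adopts the largest, 0.284, and states that "a sample size of seven per age subgroup is deemed sufficient to meet the aforementioned requirements with at least 80% power". It continues: "In anticipation of possible drop-outs or missing samples, eight subjects will be enrolled in each age subgroup". The same sentence gives a total of about 30, and the list under it ends with "Infants >12 and < 24 months, N = 6".

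Six infants is the plan elsewhere too. Section 3.1 says "approximately 6 subjects will be enrolled in Cohort 4", the synopsis sample-size list has "Infants > 12 and < 24 months, N = 6", and Section 4 gives the same number.

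Two other provisions bear on the number. Section 6.5 lets the Safety Data Review Committee recommend that "a cohort be expanded". Section 6.7.2 says "Subjects who discontinue the study due to an AE will not be replaced", but also "Subjects with serious protocol violations where PK is not evaluable will be replaced"; replacement for other reasons is at the sponsor's discretion.

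**The concern.** Section 8.2 contradicts itself. Eight in each of four subgroups is 4 × 8 = 32, whereas the list adds to 8 + 8 + 8 + 6 = 30. Cohort 4 is one below the number the section calls sufficient and two below the number it says will be enrolled. It therefore has no margin for drop-outs or missing samples, although the text claims that margin for every subgroup. No separate SD, power or reason is given for six.

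Section 8.2 is the only justification of the cohort sizes. A reader would conclude that the CL target is met with at least 80% power in all four cohorts, including the youngest, for which the synopsis says interim PK exposure estimates will be used to assess the dose.

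**Working it through.** **Inputs, all from Section 8.2.** Two-sided 95% interval; limits 60% and 140% of the geometric mean; power at least 80% per subgroup; SDs as listed above. The conversions from between-subject variability reproduce: sqrt(ln(1 + 0.29²)) = 0.2842 and sqrt(ln(1 + 0.23²)) = 0.2270.

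**Criterion (assumed, because the protocol prints no formula).** On the log scale the t-interval has half-width t(0.975, n−1) × s / sqrt(n), where s is the sample SD. Relative to the estimated geometric mean, the upper limit requires a half-width of at most ln(1.4) = 0.3365. The lower limit requires at most −ln(0.6) = 0.511. The upper limit binds.

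Power is the chance that s is small enough:

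power(n) = P[ chi-square(n−1) ≤ x ], where x = n(n−1) × (ln 1.4)² / (t² × SD²)

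**The plan's own figure first (CL, SD 0.284).** At n = 7, t = 2.4469 and x = 42 × 0.3365² / (2.4469² × 0.284²) = 9.85. On 6 degrees of freedom the power is 86.9%. The smallest n reaching 80% is seven, as the protocol states.

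**The same formula at the other sizes (CL, SD 0.284):**

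| n | t(0.975, n−1) | x | Power |
|---|---|---|---|
| 5 | 2.7764 | 3.64 | 54.3% |
| 6 | 2.5706 | 6.37 | 72.8% |
| 7 | 2.4469 | 9.85 | 86.9% |
| 8 | 2.3646 | 14.06 | 95.0% |

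A simulation of 400,000 trials applying both limits agrees: 54.4%, 72.8%, 86.9% and 95.0% (approximately, to simulation error).

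**Six subjects with the protocol's other SDs:**

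| Parameter | SD | Power at n = 6 |
|---|---|---|
| CL, noncompartmental | 0.27 | 78.3% |
| V1, population PK | 0.227 | 92.4% |
| Vdss, noncompartmental | 0.21 | 96.0% |

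The largest SD that gives 80% at n = 6 is 0.2655, below both CL SDs in Section 8.2. At n = 7 it is 0.3046.

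**Sensitivity to the formula (CL, SD 0.284):**

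| Criterion | Smallest n for 80% | Power at n = 6 |
|---|---|---|
| Log-scale t-interval, both limits (used here) | 7 | 72.8% |
| Symmetric log half-width of 0.4 | 6 | 89.1% |
| Normal quantile 1.96 instead of t | 5 | 94.8% |
| Lower limit only | 5 | 98.8% |
| Interval within 60% to 140% of the true mean | 8 | 59.8% |

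Only the first has seven as its smallest sufficient n.

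**The case against.** **The formula is inferred.** The protocol calls seven sufficient, not minimal. A symmetric half-width of 0.4 also makes seven sufficient (96.9%) and gives 89.1% at six. This stands as a condition on the 73%. It does not rescue the text: that criterion would have led to six, not seven, as the required number, and under any formula Section 8.2 shows no calculation for six and still promises eight in each subgroup.

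**A population model could do much better.** Section 8.5.6 allows population PK estimation and fits one model to all the study data. If the variance were pooled over 30 subjects (26 degrees of freedom), the same calculation at six gives 99.8%. The precision actually reached for infants may therefore differ greatly from what 73% suggests. However, Section 8.2 does not state pooling as its sizing basis, and treating each subgroup alone is the reading that reproduces seven.

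**The shortfall is modest.** It concerns one parameter. At SD 0.27 it is under two percentage points, and an SD printed as 0.27 could be as low as 0.265, which gives 80.2%. The SDs also come from healthy adults. All of this is fair, but the protocol chose 0.284 as its conservative value and made its claim on that.

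**The analysis is descriptive.** No test, stopping rule or dose rule uses the 60% to 140% target, and CL and Vdss are not among the primary variables listed in Section 8.4.2. That limits the harm; the stated power remains wrong.

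**Losses may be made good.** A discontinuation for an adverse event need not remove PK data, since Section 8.5.3 asks for only one post-dose sample and Section 5.2 continues procedures after a stopped infusion. The 54.3% at n = 5 therefore applies only if a subject is lost to the CL estimate and not replaced. Conversely, replacement restores at most the planned six, and cohort expansion is not tied to the precision target.

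**Conclusion.** The concern holds. Two statements in Section 8.2 are wrong as written for Cohort 4: that eight will be enrolled in each subgroup, which needs no calculation to see, and that the CL target carries at least 80% power in each.

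With all six infants evaluable, the chance of missing the CL target is 100% − 72.8%, about 27%. The plan allows 20%, and seven subjects would give about 13%. Volume meets its target at six, and Cohorts 1–3 at eight are unaffected. The percentages assume the log-scale t-interval criterion, each subgroup analysed alone, and an SD of 0.284 in infants. CL power at six stays below 80% at 0.27.

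**What to change.** **Section 8.2**

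- Replace the promise of eight in each subgroup with eight in each of Cohorts 1–3 and approximately six in Cohort 4, approximately 30 in total.
- State that at least 80% power for CL applies to Cohorts 1–3.
- Give Cohort 4's power with six evaluable subjects: about 73% for CL and 92% for volume. Add that CL falls to about 54% if one subject is lost and not replaced under Section 6.7.2.
- Print the criterion beside these figures: t(0.975, n−1) × s / sqrt(n) ≤ ln 1.4, with SD 0.284 for CL and 0.227 for volume. If the sponsor used another formula, print that one and its result at n = 6 instead.

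**Synopsis**

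The list already shows 8, 8, 8 and 6. Add only a note that Cohort 4 does not reach 80% power for CL, unless the sponsor's own formula shows otherwise.

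**Cost.** A few sentences in Section 8.2 and one note. One stated property becomes less favourable for Cohort 4. Enrollment, sampling and analysis do not change.
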